#### 5.2 Research Drug Information

##### ( 1 ) testing medicine

The main component is the wall-removed Ganoderma lucidum spore powder, specification : 2g / bag, batch number : the same batch number ;

##### ( 2 ) control drug

Placebo : the main component is the wall shell and accessories of the wall-removed Ganoderma lucidum spore powder, specification : 2g / bag, batch number : same batch number

##### ( 3 ) Drug source

---

The above drugs were produced and provided by Jinhua Shouxiangu Pharmaceutical Co., Ltd., and all research drug tests were qualified. If the drug expiration test is not completed, the drug needs to be re-prepared and blinded.

### 5.3 medication regimen

(1) From the first day after enrollment, the subjects were given oral research drugs ( wall-removing spore powder / placebo ), once in the morning and once in the evening, 1 packet ( 2g ) each time, for 90 days. Taking method : 50ml warm boiled water into suspension.

(2) dosage adjustment: If this scheme has not been revised in writing, the dose of the test drug shall not be adjusted.

### 5.4 drug packaging

One patient in the trial was treated with 6 medium packs of medicine, each containing 30 small bags. The drugs in the pouch are ganoderma lucidum spore powder ( 2g ) or placebo ( 2g ).

### 5.5 Drug storage and recovery

The storage conditions of the drugs studied were : closed, placed in a clean, ventilated, shady place, away from children 's contact.

All test drugs must be stored safely and sealed, kept and distributed by a special person, and supervised the subjects to take them on time as required. The researcher should register and sign the medication record form after each administration to the patient, and be responsible for recycling the used test drug packaging bags.

Researchers and sponsor supervisors must count all drugs at the end of the trial and check with the number of drugs issued, the number of missing drugs and the cause of CRF. At the end of the trial, all unused drugs should be returned to the sponsor, and the relevant handover procedures and records should be completed according to GCP requirements.

## VI.drug combination

It is forbidden to use any interfering drugs, such as biological therapy, traditional Chinese medicine treatment, antibiotic treatment, microecological modulators, antidepressants, other health care products with immune regulation function,

---

psychotropic drugs and so on.

## **VII.research process**

### 7.1 Screening / Baseline ( Week 0 )

- ( 1 ) Sign informed consent ;
- ( 2 ) Complete the verification of inclusion and exclusion criteria ;
- ( 3 ) to obtain demographic data and medical history data ;
- ( 4 ) Psychiatric examination and HAMD-24 scale evaluation ;
- ( 5 ) PSQI scale evaluation ;
- ( 6 ) Stool specimen collection ;
- ( 7 ) Thyroid function test residual blood collection ;
- ( 8 ) Women of childbearing age to do urine pregnancy test ;
- ( 9 ) Record the combined medication ;
- ( 10 ) Drug distribution.

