## IV.case selection

### 4.1 inclusion criteria

- ( 1 ) Patients with depressive symptoms after papillary thyroid carcinoma surgery in the outpatient department of Zhejiang Cancer Hospital ( patients with depressive symptoms by clinical psychiatrist and Hamilton Depression Scale score of 8-20 points ) ;
- ( 2 ) Han nationality ;
- ( 3 ) no previous depression and other mental diseases ;
- ( 5 ) 18-80 years old ;
- ( 6 ) Women ;
- ( 8 ) BMI : 19 ~ 24. ( BMI calculation method :  $BMI = \text{weight ( kg )} / \text{height}^2$  ( m ) )

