### 4.2 excluded criteria

- ( 1 ) suffering from other diseases of the intestinal system ;
- ( 2 ) Have received gastrointestinal surgery before intervention ;
- ( 3 ) Including patients with other malignant tumors, who need chemotherapy, radiotherapy, biological therapy or traditional Chinese medicine treatment ;
- ( 4 ) received antibiotics or microecological modulators within 3 months before the intervention ;
- ( 5 ) Acute intestinal obstruction ;
- ( 6 ) Patients with severe depressive symptoms who must receive antidepressant treatment ;
- ( 7 ) organic diseases such as heart and brain diseases, brain trauma ;
- ( 8 ) history of mental illness, use of psychoactive drugs such as drugs ;
- ( 9 ) Severe liver and kidney dysfunction ;
- ( 10 ) Pregnancy, lactation

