#### ( 2 ) Validity standard

Depression relief : After 90 days of treatment, HAMD score decreased.

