### **2. statistical analysis plan**

---

Statistical analysis was performed using SPSS 9.1.3 statistical software.

( 1 ) Distribution of two groups of cases : the comparison of the shedding and elimination rates of the two groups was performed by  $\chi^2$  test or exact probability method.

( 2 ) Comparability analysis : Demographic data and other basic indicators were compared to measure the comparability of the two groups. According to the type and distribution of data,  $\chi^2$  test or exact probability method, CMH test, t test, variance analysis or non-parametric statistical method were used.

( 3 ) Compliance analysis : To compare whether the two groups of patients use the test drugs on time and in quantity. The drugs that were not banned in the regimen were mainly tested by  $\chi^2$  test or exact probability method.

( 4 ) Validity analysis : Repeated measures were used to compare the differences in measurement data such as depression scores and sleep scores between the experimental group and the control group, or linear regression models were used to control baseline depression scores or sleep scores. Differences in depression scores and sleep scores between the two groups. Compare the score after the end of the experiment with the baseline score, calculate the difference before and after the change, and use the t test to compare the difference between the score changes of the experimental group and the control group.

( 5 ) Safety analysis : adverse reactions were statistically described, and the incidence of adverse reactions in the two groups was compared by  $\chi^2$  test or exact probability method.

( 6 ) All statistical tests should give test statistics and corresponding p values. When using the exact probability method, the p value is given directly.  $P \leq 0.05$  indicated that the difference was statistically significant.

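### The plan names no use for the thyroid function results implied at Week 0 and Day 90, leaving avoidable noise in the arm comparison and an unmeasured common cause in the mechanism analyses

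*Combined protocol and SAP*

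**What the plan says.** Section 4.1(1) recruits "Patients with depressive symptoms after papillary thyroid carcinoma surgery in the outpatient department". Neither 4.1 nor 4.2 mentions thyroid function. Exclusion 4.2(7) covers "organic diseases such as heart and brain diseases, brain trauma", a list given by example and so not closed.

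Sections 7.1(7) and 7.3(4) both list "Thyroid function test residual blood collection", at Week 0 and Day 90; the item is absent at Day 28. Section 7.4(3) describes how the leftover blood is separated and frozen and says nothing about the thyroid values. Section VI states "It is forbidden to use any interfering drugs"; thyroid hormone is not among its examples. Concomitant medication is recorded at all three visits.

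The efficacy standard in 8.1(2) is "Depression relief : After 90 days of treatment, HAMD score decreased", with no threshold and no reference to the control arm. For the comparison, X.2(4) offers repeated measures or a regression in which "linear regression models were used to control baseline depression scores or sleep scores", and also says to "use the t test to compare the difference between the score changes of the experimental group and the control group". Under X.2(2), "Demographic data and other basic indicators were compared to measure the comparability of the two groups"; the indicators are not listed. Time since surgery appears only in the full analysis set definition in X.1(1), as a minimum of one month with no upper limit.

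**The concern.** Thyroid status is an obvious candidate prognostic factor after thyroid surgery. If it influences mood, sleep, metabolites or gut flora, and differs between patients or shifts during the 90 days, three things follow.

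- The comparison between arms carries variation that a baseline covariate could remove.
- A patient's HAMD-24 score could fall for a reason unrelated to either product and still count as relief under 8.1(2).
- Section II aims to clarify the antidepressant mechanism by combining metabolomic and flora data with clinical data. An association across patients between metabolite change and HAMD-24 change is not a randomised comparison, so a factor that moves both can produce it.

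The plan implies that the relevant test is run twice but names no thyroid variable with which to examine any of this.

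**Working it through.** **Inputs.** The plan gives no figure on this point. From 5.1: 200 experimental and 100 control patients. Assumed, with no source in the documents: partial correlation r of baseline thyroid function with Day 90 HAMD-24, given baseline score, of 0.1 to 0.4; HAMD-24 SD of 4; baseline to Day 90 correlation of 0.5.

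**1. Precision.** Adjustment multiplies the standard error by √(1 − r²).

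| r | √(1 − r²) | SE reduction |
|---|---|---|
| 0.1 | 0.995 | 0.5% |
| 0.2 | 0.980 | 2.0% |
| 0.3 | 0.954 | 4.6% |
| 0.4 | 0.917 | 8.3% |

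For an effect that has 80% power without the covariate (two-sided 0.05), power becomes 80.4% at r = 0.1 and 86.4% at r = 0.4.

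**2. Chance imbalance.** The SD of the standardised difference in a covariate between arms is √(1/200 + 1/100) = 0.1225, so the 95% limit is 1.96 × 0.1225 = 0.24 SD. A partial correlation goes with the residual SD, 4 × √(1 − 0.5²) = 3.46. At r = 0.3 the shift at that limit is 0.24 × 0.3 × 3.46 = 0.25 points. Using the full SD of 4 gives 0.24 × 0.3 × 4 = 0.29 points.

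A second route treats thyroid status as normal or abnormal. With 10% to 40% abnormal at baseline (assumed), the 95% chance imbalance is 1.96 × √[p(1 − p)(1/200 + 1/100)], or 7 to 12 percentage points. If normalisation shifts HAMD-24 by 1 to 4 points (assumed), the distortion at the 95% limit is 0.07 to 0.47 points. The expected value is zero on both routes.

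**3. Scale.** With residual SD 3.46, the SE of the arm difference is 3.46 × 0.1225 = 0.42, and the 95% half-width is 1.96 × 0.42 = 0.83 points. The 0.25-point shift lies well inside that.

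**4. Mechanism associations.** Suppose a thyroid measure correlates a with metabolite change and b with HAMD-24 change, and nothing else links the two. They then correlate at a × b. Taking 0.1 to 0.4 for each (assumed) gives 0.01 to 0.16. With 300 patients the approximate SE of a correlation near zero is 1/√(300 − 3) = 0.058, so about 0.11 reaches P = 0.05. At the upper end of the range, thyroid status alone could produce a nominally significant association; at the lower end it would be negligible.

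**The case against.** The strongest reply is that the placebo arm already deals with the matter. Section III describes a randomised, double-blind, placebo-controlled trial and X.2(4) compares change between arms. A thyroid-related fall that occurs whichever product is taken cancels in expectation, and the remaining chance imbalance is covered by the confidence interval. This stands. A reader might infer that a product effect cannot be told apart from a thyroid effect; for the randomised comparison the documents do not support that. It relies on allocation being random. Section XI.1 forms groups by order of enrolment, which is a separate question and not a thyroid issue.

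A reader might also infer that eligibility is at fault and that a patient with overt hypothyroidism is plainly admitted. Exclusion 4.2(7) is open-ended, so the documents leave this unspecified. Nor can it be shown that the trial keeps only the leftover blood: the CRF is not among the documents, medical history and concomitant medication are recorded, and the baseline indicators in X.2(2) could include thyroid function. What remains is that no section names the result as something to record or analyse.

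The clinical premise is also absent from the documents. They do not say that patients have abnormal thyroid function, that it affects HAMD-24, or that it changes within 90 days. The benefit could be close to nil.

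Finally, a baseline covariate cannot remove the effect of thyroid change during treatment. That is true. Day 90 values arise after randomisation and should not enter the efficacy model, so the fix narrows the mechanism question without closing it.

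**Conclusion.** The point holds as an inexpensive improvement, not as a threat to the validity of the arm comparison. Under the stated assumptions the omission costs about 0.5% to 8% in standard error, and a chance shift of roughly 0.25 to 0.3 points at the 95% limit of imbalance when r = 0.3. Both figures rest on correlations and SDs that the plan does not give.

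The firmer part concerns what randomisation does not protect: the within-patient fall in 8.1(2) and the metabolite and flora associations in Section II. There, thyroid status is a possible common cause for which the plan names no variable. Whether it operates in these patients is unknown from the documents, and the plan as written would not provide for finding out.

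**What to change.** - Record in the CRF the Week 0 and Day 90 thyroid function results, naming the analyte in advance (for example TSH), and time since surgery. The last is already needed to apply the full analysis set definition in X.1(1).
- Before unblinding, name the baseline-adjusted regression in X.2(4) as the model for HAMD-24 and PSQI, with baseline thyroid function and time since surgery added to baseline score. The present wording also allows repeated measures and an unadjusted t test, so adding covariates to one option would leave the others unadjusted.
- Include baseline thyroid function in the models relating metabolites or flora to HAMD-24.
- Add a sensitivity analysis restricted to patients whose baseline result lies within the laboratory's reference range, and report how many remain. The subset is defined at baseline, so the comparison between arms stays valid.
- Report Day 90 thyroid results by arm, descriptively only.

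The cost is a few CRF fields from tests already implied and two terms in the efficacy model, with no new sample and no extra patients. No eligibility or treatment rule changes.

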### 7.2 Visit 1 (D28±3d)

- ( 1 ) Evaluation of HAMD-24 scale ;
- ( 2 ) PSQI scale assessment ;
- ( 3 ) Record drug combination and adverse events ;
- ( 4 ) Drug recovery and distribution.

### 7.3 Visit 2 (D90±3d)

- ( 1 ) Evaluation of HAMD-24 scale ;
- ( 2 ) PSQI scale assessment ;
- ( 3 ) Fecal specimen collection ;
- ( 4 ) Thyroid function test residual blood collection ;
- ( 5 ) Record the combined medication and adverse events ;
- ( 6 ) Drug recovery.

### 7.4 Principles of index collection

( 1 ) Hamilton Depression Scale ( HAMD-24 ) score and Pittsburgh Sleep Quality Index score :

The HAMD-24 was evaluated by two senior clinical psychologists, who were responsible for the assessment of HAMD-24 by [name]. PSQI was evaluated by

---

the subjects themselves and guided by psychologists.

(2) Fecal sample collection method :

①The stool collector was placed in the toilet, the feces were discharged into the collector, and the fresh fecal samples were fully mixed with a slender handle spoon ( Note : to avoid urine contaminated feces ).

②The mixed fecal samples were divided into two 5 ~ 10 mL sterile tubes marked with good names or pre-sterilized collection tubes, and about 2 ~ 3 mL of each tube was collected.

③About 1 ml fecal samples were sub-packed into 1.5 ml centrifuge tubes from 5-10 ml sample collection tubes with long-stem wooden rods. Or take about 1 ml to 1.5 ml centrifuge tube directly from the mixed fecal samples in 1.

④The centrifuge tube was covered well, and the fit was checked. According to the numbering order, it was placed in the sample box and placed in a refrigerator at -80 ° C for cryopreservation.

If the feces are collected at home, the collection tube is packed with a self-sealing bag and sent to the hospital sample receiving place as soon as possible ( within two hours ).

Notes for sample collection and preservation :

Samples should not be exposed to room temperature for more than 2 hours.

Sample collection should be carried out at the same time of the day to avoid the influence of rhythm on metabolism.

The sample should be mixed immediately after collection, and frozen after separation.

Prepare two samples at the same time to avoid repeated freezing and thawing.

(3) Blood sample collection:

①The remaining venous blood after thyroid function test in the laboratory was injected into the serum / plasma separation tube, and mixed upside down for 5-8 times.

②The whole blood was placed at room temperature ( 20 ° C ~ 25 ° C ), standing for about 30min ( no more than 2h ), and the blood was completely solidified,

---

and the anticoagulant was added as plasma.

③ After the serum / plasma was fully separated, centrifuged at 1000 g for 10 min. About 500  $\mu$  l-1mL of the supernatant was taken to a 1.5mL centrifuge tube ( recommended multi-tube subpackage ) and placed in a cryopreservation box.

④. The cryopreservation box was placed in a refrigerator at  $-80^{\circ}\text{C}$  and sent by dry ice.

( 4 ) Stool and blood samples preservation and transportation: ①Liquid nitrogen rapid cryopreservation for 15 min and then transferred to  $-80^{\circ}\text{C}$  refrigerator cryopreservation.②Ensure that the refrigerator continues to work constantly power, power will cause the sample freeze-thaw③Shunfeng and other dry ice transport ( in transit 5kg / day ) or cold chain transport.

## **VIII.response evaluation criteria**

### 8.1 leading indicator

#### ( 1 ) Hamilton Depression Scale ( HAMD-24 ) score classification

No obvious depressive symptoms : total score 0-7 points ; may have depression : total score 8-20 points ; mild or moderate depression : total score 21-35 ; severe depression : total score 36-76 points.

#### ( 2 ) Validity standard

Depression relief : After 90 days of treatment, HAMD score decreased.

### 8.2 secondary index

#### ( 1 ) Changes of intestinal microbial diversity and metabolites in patients

( 2 ) Remission of sleep status : After 90 days of treatment, the Pittsburgh Sleep Quality Index score decreased.

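### Section 8.2(2) counts any fall in PSQI at 90 days as sleep remission, a rate that would be substantial in both arms with no true effect and that X.2(4) has no plan to analyse

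*Combined protocol and SAP*

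**What the plan says.** All references are to the combined protocol and SAP.

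- **Endpoint.** Section 8.2(2), a secondary index: "Remission of sleep status : After 90 days of treatment, the Pittsburgh Sleep Quality Index score decreased". Nothing is said about how large the fall must be, or what score must be reached.
- **Entry.** Section 4.1 selects on depression: "patients with depressive symptoms by clinical psychiatrist and Hamilton Depression Scale score of 8-20 points". Neither 4.1 nor 4.2 mentions sleep. Section 7.1 lists "PSQI scale evaluation" at baseline, and PSQI is repeated at D28 and D90 (7.2, 7.3), but it plays no part in eligibility.
- **Analysis.** Section X.2(4) begins: "Repeated measures were used to compare the differences in measurement data such as depression scores and sleep scores". It then offers an alternative, "or linear regression models were used to control baseline depression scores or sleep scores", and adds an analysis of change from baseline: "use the t test to compare the difference between the score changes of the experimental group and the control group". None of these is named as the analysis of 8.2(2).
- **Tests of proportions.** Section X.2 assigns chi-square or exact tests to dropout and elimination, baseline comparability, compliance and adverse reactions. A sleep remission proportion is not among them.
- **Main endpoint.** Section 8.1(2) uses the same any-fall form for HAMD.

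**The concern.** Two separate things are wrong.

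First, the label. PSQI is a whole-number score from 0 to 21 and varies between visits even in a stable patient. If every fall counts, a patient going from 16 to 15 has remitted. So has a patient who slept well at baseline and drops by one point, while a patient at 0 cannot remit at all. A reader of the report would take a sleep remission rate to mean resolved sleep disturbance. Under this rule it would largely reflect visit-to-visit variation and regression to the mean.

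Second, the mismatch. Section 8.2(2) defines a yes/no outcome that has no planned analysis, and X.2(4) lists continuous analyses without naming any as the endpoint. The analyst could choose among a responder rate, a repeated-measures comparison, a baseline-adjusted regression and a change-score t test after seeing the data.

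**Working it through.** **The plan's own figure.** The only sample-size derivation (section 5.1) starts from 100 pairs with 15% dropout. 100 / (1 − 0.15) = 117.6, against a stated 117, so it reproduces to within rounding. It has no bearing on PSQI: no PSQI mean, SD, correlation, effect size or power is stated anywhere.

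**Inputs from the plan.** 200 experimental and 100 control (5.1). With 15% dropout, 0.85 × 200 = 170 and 0.85 × 100 = 85 completers. A p-value of 0.05 or less "indicated that the difference was statistically significant" (X.2(6)); two-sided testing is assumed because sidedness is not stated.

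**Inputs assumed.** PSQI mean 7, SD 3-3.5, baseline-to-D90 correlation r of 0.5-0.8, whole-number scores limited to 0-21.

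**Step 1: share with a fall when nothing changes.** For a whole-number score, P(fall) ≈ Φ(−0.5 / SD of change), where SD of change = SD × √(2(1 − r)).

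| SD | r | SD of change | P(fall) |
|---|---|---|---|
| 3 | 0.5 | 3.00 | 43% |
| 3 | 0.8 | 1.90 | 40% |
| 3.5 | 0.5 | 3.50 | 44% |
| 3.5 | 0.8 | 2.21 | 41% |

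This gives 40-44%. At r = 0.9 simulation gives 36-37%. Setting the SD of change directly gives 31% at 1 and 37% at 1.5. Imposing the 0-21 limits, with assumed baseline means from 3 to 10, gives 30-32% at an SD of change of 1 and 41-43% at 3. If both arms drift down by one point, simulation gives 55-60% at correlations 0.5-0.8.

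**Step 2: who is counted.** With no true change and r of 0.5-0.8, simulated patients starting at 10 or above are counted as remitted 58-73% of the time. Those starting at 5 or below are counted 20-26% of the time. The label largely tracks the baseline score.

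**Step 3: power of the possible analyses.** Assume a true 1-point difference, SD 3, a half-point fall common to both arms, and 170 vs 85 completers. Let k = √(1/170 + 1/85) = 0.1328.

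- Change-score t test: Φ(1 / (3√(2(1 − r)) × k) − 1.96). At r = 0.5 the SE is 3 × 0.1328 = 0.3985, 1 / 0.3985 = 2.51, and Φ(0.55) = 71%.
- Baseline-adjusted regression: Φ(1 / (3√(1 − r²) × k) − 1.96). At r = 0.5 the SE is 2.598 × 0.1328 = 0.3451, 1 / 0.3451 = 2.90, and Φ(0.94) = 83%.
- Any-fall comparison at r = 0.5: control Φ((−0.5 + 0.5) / 3) = 50%, experimental Φ((−0.5 + 0.5 + 1) / 3) = 63%. A two-proportion test then has about 51%.

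Simulation with rounding and the 0-21 limits gives:

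| r | Any fall | Change-score t test | Baseline-adjusted regression |
|---|---|---|---|
| 0.5 | 50% | 69% | 80% |
| 0.6 | 62% | 79% | 88% |
| 0.7 | 69% | 87% | 93% |

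Repeat runs moved these by up to about 3 points, most in the any-fall column. At r = 0.5 the gap between regression and any-fall is 80 − 50 = 30 points. Of that, 80 − 69 = 11 points is regression against the change-score test, and only 69 − 50 = 19 is dichotomisation.

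**The case against.** The strongest reply is that the definition does no harm to the planned inference. X.2(4) analyses sleep as a continuous score and names no test of the proportion. A reader might infer from 8.2(2) that power is lost and most of the information in the score discarded. The documents do not support that, because the responder test in question is not in the plan. This part of the reply stands.

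A reader might also infer a biased comparison. That does not follow either: in a randomised, double-blind, placebo-controlled trial the noise raises the any-fall share in both arms alike.

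Nor is 40% a fact about this trial. It needs an SD of change of about 2 or more, which the documents do not give. Under the LOCF rule in section X.1, patients lost before D28 would carry baseline forward and show no fall. If all of the assumed 15% did so, 40-44% would become 0.85 × 40 = 34% to 0.85 × 44 = 37%.

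The missing sleep criterion at entry is not an error in itself. The trial recruits on depressive symptoms, and a secondary scale needs no threshold. It matters only because the word remission presumes a problem to remit from.

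Finally, 8.2(2) may be meant only to state the direction of benefit, with remission a loose translation of improvement. That is possible, but the text does not say so, and it is the only definition of the sleep endpoint. Even on that reading, X.2(4) still does not say which analysis answers it.

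**Conclusion.** The point holds as a problem of endpoint definition and of mismatch with the analysis section. Following 8.2(2) literally would label roughly 3 to 4 in 10 patients in each arm as remitted with no true effect: 40-44% under SD 3-3.5 and correlation 0.5-0.8, 31-37% under an SD of change of 1-1.5. All of these inputs are assumptions. It does not extend to a biased treatment comparison, and dichotomisation loses power only if the rate itself is tested.

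The choice left open in X.2(4) has a modest price of its own. Under the assumptions in step 3, baseline-adjusted regression has about 80-93% power against 69-87% for the change-score t test, a difference of 6 to 11 points. An any-fall comparison would have about 50-69%.

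This is a secondary endpoint, so the trial's main conclusion does not rest on it. The correction should be made because it is nearly free and removes a misleading result. The same wording in 8.1(2) matters more.

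**What to change.** 1. Replace 8.2(2) with: *Difference between arms in mean PSQI at D90, adjusted for baseline PSQI (linear regression as in X.2(4)), with 95% CI.*
2. In X.2(4), name that regression as the sleep analysis, so that the other listed methods are not open alternatives.
3. Delete the rule that any decrease is remission. The share of patients with any fall may be shown descriptively by arm, but not called remission.
4. Correct the any-fall wording for HAMD in 8.1(2) at the same time.

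The cost is a sentence in 8.2 and the selection of a model already listed. No new data or visits are needed, since PSQI is already collected at baseline and D90. The downside is that the report loses a remission percentage.
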